6.3.4 CHW Supervision

CHWs are not clinicians and they often struggle with many of the same issues as their clients in terms of health problems, children, housing, and poverty. This allows them to intimately understand the challenges their clients face and usually translates into strong bonds between CHWs and clients, but it sometimes transforms into a tremendous burden when clients struggle with serious issues. The CHWs also must deal with the stresses of home visitation (safety, cleanliness, hectic households, and poverty). In order for CHWs to successfully perform their job, they require adequate supervision and support. Supervision is best conducted using a team approach with a group of CHWs in order to facilitate self-discovery and group learning. In this trial, CHWs will report directly to the Erie AE-C for day-to-day supervision and support as needed. Every two weeks, CHWs and the Erie AE-C will also meet with [name] and/or [name] for discussion of clinical issues, self-management skills support, and for continuing education. [name] or an Erie mental health provider will meet with CHWs once a month to discuss mental health issues related to participants or the CHW job and to generate strategies for resolution.

6.4 Comparison Arm: Clinic-based AE-C Education

6.4.1 AE-C Training: Most candidates for the AE-C certification have prior experience as an asthma educator and therefore require only a preparatory course to pass the certification exam. Erie leadership will identify the appropriate candidate for this position. This person will then complete a 2-day comprehensive workshop offered in Chicago by the Respiratory Health Association (www.lungchicago.org/certified-asthma-educator-training/). If further training is required, an additional online course if available through the American Association of Respiratory Care (www.aarc.org/education/asthma_ course). Once this person has passed the AE-C certification exam, he/she will complete a subsequent 2-day training with the research investigators to familiarize him/her with the intervention expectations and protocol. The AE-C may start delivery of intervention before obtaining formal AE-C certification as long as they have completed a training course and the study-specific training.

6.4.2 AE-C Intervention Protocol: The AE-C will receive contact information and have access to the clinical chart for participants randomized to the AE-C arm. The AE-C will schedule the participant's family to come in for an educational session in the clinic. At this visit, the AE-C will assess and educate on asthma symptoms, control, triggers, medication technique, adherence, presence of a written asthma plan, and he/she will address caregiver/child concerns. The AE-C will call the family on the telephone in 2-4 weeks to discuss self-monitoring of symptoms and medication and answer any questions. The AE-C will schedule the participant's family again to come in for a similar visit at 6-months. A follow-up telephone call will occur 2-4 weeks later.

6.5 Standard and Research Procedures

The AE-C is considered "best practice" but is not routine care at Erie due to funding. For this study, the AE-C condition is subsidized by the research budget making it a research procedure that will not be offered to intervention arm participants. CHW intervention is a research procedure. Both interventions will be documented in the medical record; support staff regularly document patient encounters in the record, making this standard procedure. The data collection is a research procedure.

6.6 Fidelity and Process Measures: Training: The CHWs will be assessed at the end of the trainings using role plays to determine that they have adequate knowledge and intervention delivery skills. The AE-C will have passed the National Asthma Education Certification Board (NAECB) examination. Delivery: CHWs and the AE-C will complete documentation after every encounter to record curriculum topics covered, resources utilized, and issues encountered after home and clinic visits. These will be reviewed monthly by unblinded staff to ensure fidelity and also to inform the study team on areas of focus and challenge. The data will also be used in final analyses to determine “dose” of intervention and to assess the influence of specific topics/skills on outcomes. Additionally, CHW and AE-C documentation in the EMR will be reviewed quarterly to capture frequency of interactions between clinicians, CHWs and AE-C, behavioral health providers, and case management, and the topics covered. Home visits and clinic visits will be randomly tape recorded and reviewed by unblinded staff to ensure intervention fidelity and accuracy of CHW/AE-C documentation.

6.7. Retention: Participants will be contacted by UIC research staff monthly to verify contact information. We will obtain multiple alternative contacts at the time of enrollment – friends, family, or others likely to keep in touch with the participant and know their whereabouts. We can also search the clinic records for changes in address or telephone number. Incentive payments for data collection aid in retention. The one source that will not be utilized will be the CHWs as this approach could lead to differential ascertainment of outcomes between the arms and introduce bias into the study.

6.8. Outcomes:

6.8.1. General Procedures

Individual outcomes will be collected in the homes by UIC RS. Results will not be returned to participants or their clinicians in order to simulate routine clinical care as much as possible. Emergency plans will be implemented if outcomes are in critical ranges. For example, endorsing a suicide plan will receive immediate intervention and appropriate referrals.

6.8.2. Instruments

The instruments and data domains are in the following table. All instruments have been validated, most with official Spanish validations as well. All instruments will have both English and Spanish translations. Before the study begins, the RSs will receive training sessions which will cover the procedures involved in data collection. The RSs will perform several “test” data collections in both English and Spanish, where they will perform data collection with volunteers. The data collection process and instruments will be reviewed by study staff and then compared to determine intra- and inter-rater reliability. Problems with question accuracy and translations will be fixed.

6.8.3. Salivary Cotinine Protocol:

The salivary cotinine assay will be performed by staff in the UIC Department of Pediatrics laboratory of [name] and UIC Research Resource Center – [name].

Equipment: bioquant ELIZA assay. 360/kit (96 wells), capped test tubes.

Procedure:

1. Nothing to drink for 1 hour before
2. Spit into tube (If dry mouth, have them not swallow for a minute and then try.)
4. Need 1 ml

5. Cap tube
6. Transport to UIC within 24 hours
7. Store at -20 degrees Celsius until transport to lab for analysis

OUTCOME ASSESSMENTS

Domain	Questions	# of items	Pre-base line (phone or in person)	0mo Base line	6mo	12mo	18mo (phone or in person)	24mo
Screening	Erie pre-screen							
	UIC screen	21,17,10						
Asthma Control	Activity limitation over 14 days ⁴²⁻⁴³	1						
	ACQ ¹⁴⁻¹⁷	6						
	CACT/ACT ²⁰⁻²⁴	5-7						
	Oral steroids* ^{13,20}	1						
	Asthma functional severity scale ²⁵	6						
Asthma Medicines	Caregiver self-report ¹⁰	5						
	Child self-report ¹⁰	3						
	Observed medicines ¹⁰	2						
	Observed technique ¹⁰	11, 12, 10						
	Adherence ¹⁰	5						
Triggers	Home assessment (self-report + observed) ^{11,19}	167						
	Salivary cotinine ^{11,26}	1						
Health Services Utilization	Urgent care visits*	1						
	Emergency dept visits*	1						
	Hospitalizations*	1						
	Missed school*	1						
	Missed work*	1						
Demographics	Height/weight	2						
	Demographics	27						
Psychosocial	Caregiver depression PHQ-9	9						
	Child depression (CDI-2 short or parent PROMIS parent proxy) ²⁷⁻²⁹	6						
		13						
	Perceived Stress Scale 4-item ³⁵⁻³⁷	4						
	Caregiver trauma ³⁸⁻⁴⁰	6						
	Child trauma PROPS/CROPS ⁴¹	26						
	Asthma-Related Trauma Event Items	9						
	Social Support PROMIS Scale ²⁹⁻³⁴	8						
Implementation	Intervention tracking	19						

6.8.4. Mental Health Protocol:

Part 1: In the home – Research Specialists

A mental health services list will be prepared that explains how to get mental health services at Erie, as well as other local resources. This will be given to all families.

The UIC research specialist (RS) will administer all depression and trauma instruments either via a computer (handing the computer to the participant to complete) or via a paper version with pen/pencil. All instruments will be in the preferred language. They will be instructed to complete the questionnaire on their own but they can ask questions.

The RS will give the caregiver the PHQ-9 and Short Form of the PTSD Checklist - Civilian Version. In addition, if the child is unable to complete the CDI-2 Brief, the research specialist will give the caregiver the PROMIS Parent Proxy questionnaire. The RS will give the child the CDI2 Brief and the CROPS. There is no immediate scoring of these instruments. When the participant finishes completing the PHQ-9, the RS should check to see if they answered 1, 2, or 3 on question 9. If yes, then implement Suicide Protocol.

Suicide Protocol: The RS will tell the participant the following statement: "*I feel that you may need to speak to someone immediately and I am going to make a phone call so that you can speak to a professional about how you are feeling.*" The RS will call the National Suicide Prevention Lifeline and ask the participant to talk with them: [name]. If they are English-speaking, can call locally [contact]. Wait while participant completes call, but try to give privacy. Give hotline card. Give family mental health services list. If further assistance is needed, the RS should do what they feel is appropriate or contact the PI if unsure how to proceed. If participant refuses to talk with the hotline, leave them the mental health services list. Call them back 24 hours later to reinforce that we feel they need to contact this number.

Part 2: After data collection – Research Specialists

The mental health instruments should be scored within 7 days of collection. The following are abnormal scores. If participants score in these ranges, the RS is responsible for trying to call back the participant within 24 hours of noting an elevated score using the below script as a guide. The RS must inform [name] of the scoring and action within 24 hours of noting an elevated score.

- PHQ-9: ≥ 10
- Short Form of the PTSD Checklist - Civilian Version: If score ≥ 14 ,
- CDI2: If the scoring puts the child in the Elevated to Very Elevated range

"This is from the Asthma Action at Erie Trial. I was at your house a few days ago. Some of the information we collected tells us that you have [your child has] been feeling somewhat sad and anxious. Everyone feels sad or anxious sometimes but this usually only lasts a short time. We are concerned that your [your child's] feelings of sadness and anxiety are lasting too long and may be interfering in your [his/her] life. Sometimes professional help from a counselor or a doctor can help a person feel happier about life. We recommend that you call one of the people listed on the mental health services list we gave you. The people there can talk to you more about this and get you help if you need it."

For enrolled children in elevated range: All enrolled children are patients at Erie (see inclusion criteria) and therefore qualify for behavioral health services at Erie. If children are already receiving behavioral health services per caregiver report, the caregiver should be advised to talk with their provider about the results of this screen. If children are not already receiving services, the caregiver should be advised to ask at Erie about receiving services.

For caregivers in the elevated range: If caregivers are patients at Erie, they will be advised to seek behavioral health services from Erie. If they are already receiving services, they will be advised to talk with their provider about the results of this screen. If they are not patients at Erie, they will be referred to other providers on the mental health services list.

Part 3: Interventionists – AE-C and CHWs

The AE-C and CHWs will not have access to the mental health screening results and they will not conduct formal mental health screening. If they develop concerns for the children or their caregivers in regards to mental health, they will encourage them to seek services using the mental health services list. If they already receive services, they will encourage them to talk with their provider. If the AE-C or CHW has strong concerns regarding an enrolled child, they will notify the child's primary care provider to refer the child to the Erie Behavioral health program.

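### The PROMIS Parent Proxy, which stands in for the CDI-2, has no abnormal range in section 6.8.4, so a high proxy score requires no call-back; the CROPS, secondarily, has none either

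*Combined protocol and SAP*

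**What the plan says.** Section 6.8.4 Part 1 has the RS give five depression and trauma instruments. The caregiver completes the PHQ-9 and the short form of the PTSD Checklist. For the child: "The RS will give the child the CDI2 Brief and the CROPS. There is no immediate scoring of these instruments". The fifth is a substitute: "if the child is unable to complete the CDI-2 Brief, the research specialist will give the caregiver the PROMIS Parent Proxy questionnaire".

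Part 2 has the mental health instruments scored within 7 days of collection. It then gives the action rule: "The following are abnormal scores. If participants score in these ranges, the RS is responsible for trying to call back the participant", with a 24-hour limit that runs from noticing the elevated score. Three ranges follow: PHQ-9 of at least 10, PTSD short form of at least 14, and "CDI2: If the scoring puts the child in the Elevated to Very Elevated range". The RS must also report the score and the action taken to a named study team member within 24 hours. A later paragraph sets out the advice for caregivers of enrolled children in the elevated range: speak to the child's current behavioral health provider, or ask at Erie about services.

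The default outside this route is in section 6.8.1: "Results will not be returned to participants or their clinicians in order to simulate routine clinical care as much as possible". Section 11.2 names mental health risk as one of two primary risks of the trial and relies on section 6.8.4 to manage it.

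**The concern.** The proxy exists to take the place of the CDI-2, but the safety step attached to the CDI2 does not carry over to it. Whether a child's high depression score obliges anyone to act then depends on which form was used. Study staff will score the proxy within 7 days and could hold a high result with no written duty to respond. Results are not returned by default, and under Part 3 the AE-C and CHWs do not see the screening results.

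What is at stake is a prompt to the family. The caregiver filled in the proxy and already has the mental health services list. What may not reach the caregiver is word that the answers amount to an elevated score, and the advice on behavioral health services that goes with it.

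The CROPS raises a similar but weaker question. A caregiver's trauma score can trigger a call; a child's cannot.

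**Working it through.** The plan states no figure on this point and no formula applies. The check sets the instruments given in 6.8.4 Part 1 against the ranges in Part 2, and looks through the rest of the document for any other range.

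| Instrument (Part 1) | Completed by | About | Range in Part 2 | Range elsewhere |
|---|---|---|---|---|
| PHQ-9 | caregiver | caregiver | at least 10 | none needed |
| PTSD Checklist short form | caregiver | caregiver | at least 14 | none needed |
| CDI2 Brief | child | child | Elevated to Very Elevated | none needed |
| PROMIS Parent Proxy | caregiver, if the child cannot do the CDI-2 | child | none | none |
| CROPS | child | child | none | none |

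**Count by instrument.** Five are given and three have a range, so 5 − 3 = 2 have none. Of the three about the child, one has a range.

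**Count by person.**
- Caregiver: 2 of 2 own scales can trigger a call.
- Child who completes the CDI2: 1 of 2 (CDI2 yes, CROPS no).
- Proxy-rated child: 0 of 2 if the CROPS is completed, 0 of 1 if it is not.

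**Is the list open?** It is introduced as the abnormal scores, without wording such as for example or including, and the call script follows directly after the third entry. The paragraph on enrolled children in the elevated range adds no range of its own.

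**Is there an earlier instrument check for the child?** No. Part 1 rules out immediate scoring. The one item checked in the home is on a form the caregiver completes: "When the participant finishes completing the PHQ-9, the RS should check to see if they answered 1, 2, or 3 on question 9".

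**What a high score requires.** An elevated CDI2 requires (1) an attempted call, (2) a report of score and action, and (3) the child advice. A high proxy score requires none of the three. A child with a normal CDI2 and a high CROPS also requires none; a child who is elevated on the CDI2 as well is called on that account.

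**How many children?** This cannot be worked out. The document gives neither the share of children who will be proxy-rated nor the share who will score high. Eligibility starts at age 5, so use of the proxy is foreseeable. Section 2.0 reports signs of depression in 68% of teens and 59% of caregivers in the investigators' earlier trial. Those figures show that elevated scores are realistic in a related population, but they do not estimate the rate in proxy-rated children.

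**The case against.** The strongest case on the other side has four parts.

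*Other safeguards exist.* Every family receives the services list. Under Part 3, an AE-C or CHW with any concern encourages the family to seek services, and there is a second tier: "If the AE-C or CHW has strong concerns regarding an enrolled child", the child's primary care provider is notified. Section 6.8.5 makes UIC and Erie staff mandatory reporters of abuse and suicidal ideation; this covers the RSs and covers children. Section 6.8.1 provides emergency plans for outcomes in critical ranges, which it does not define. All of this stands, and it means a reader should not infer that proxy-rated children are unprotected. But none of these routes is tied to a defined proxy or CROPS score, so they reduce the consequence without closing the gap.

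*The text does not forbid a call.* This also stands. A reader might infer from the list that staff may not call about a high proxy or CROPS score. The wording supports only that they are not required to.

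*The CROPS omission may be a choice.* It is an additional trauma scale, not a replacement for a listed one, and the investigators may have meant to act only on depression scores for children. The document gives no reason either way, so it does not support calling this an error. The argument does not reach the proxy, which substitutes for a scale that is a trigger.

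*The consequence is small.* The call is an attempt, with a script that points to a list already in hand, and for the proxy it goes to the person who gave the answers. Parent report and self-report also need not share a common metric. These are fair limits on the weight of the point. A caregiver whose own score is high is called in any case, but about the caregiver.

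**Conclusion.** The point holds for the PROMIS Parent Proxy: no call-back, report or behavioral health advice is required for a high score on the form that replaces the CDI-2, although the CDI2 itself would require all three. It holds secondarily for the CROPS, as an unexplained omission that may be intended.

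The size is a count of triggers: none for a proxy-rated child, against one of two for a child who completes the CDI2 and two of two for a caregiver. The number of children concerned is unknown. The conclusion rests on reading the Part 2 list as complete, which its wording supports, and on the absence of any other range in the document.

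A reader might infer that the gap could bias the trial result. The document does not support that: the screening and call-back rules are the same for both arms, and the RSs who apply them are to be blind to arm. The point touches no sample size, power or error rate and has no effect on the CHW versus AE-C comparison. It is a modest participant-safety matter and a cheap improvement.

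**What to change.** In section 6.8.4 Part 2:

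- Add a pre-specified elevated range for the PROMIS Parent Proxy, as the counterpart of the CDI2 trigger. The document contains no cut-off, so none is proposed here; the investigators should choose one in advance and record it.
- For the CROPS, either add a range in the same way or state that it is not a call-back trigger and why.
- Apply the steps already in place to any score that becomes a trigger: scoring within 7 days, a call attempt within 24 hours of noting the score, the report of score and action, and the existing advice for enrolled children.

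The cost is a few lines of text and an IRB amendment. The script and the child advice are already written. The downside is some additional calls, part of them for false-positive scores, a trade the protocol already accepts for the three listed scales.

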6.8.5. Participant and Staff Safety

Working with CHWs poses multiple unique challenges since the CHWs are lay people that interact with participants in their homes. This study proposes the following:

Mandatory reporting: UIC and Erie staff are mandatory reporters of domestic abuse, child abuse and suicidal ideations. If a CHW or RS witness or suspect any of these situations, they will call 911 if they have concerns for the immediate safety of the person involved. If they feel safe leaving without calling 911 but have suspicions of abuse or suicidal ideation, they will bring the concern directly to their supervisor. The supervisor will review the situation, confer with the PI if needed, and determine if the police or Child Protective Services need to be notified. If the supervisor decides the situation requires reporting, the supervisor or PI will perform the reporting and also inform the participant of the decision to do so. This process will be stated in the consent form.

Staff safety: CHWs and RSs will usually visit homes alone but they will always have the option of being accompanied by a "sentry" for safety reasons. If they feel threatened or unsafe, they will not enter the home or they will leave the home. They will then notify the PI or their supervisor and home visits for that participant will be suspended until the home is determined to be safe.

Participant safety: Participants will be informed at the start of the study that if they do not feel comfortable with their RS or CHW, they can refuse them entrance into their home. Participants will be encouraged to notify the RS or project manager if they are uncomfortable with their RS or CHW. If this occurs, they will be offered the option of changing RSs or CHWs, or withdrawing from the study.

Asthma safety: CHWs and RSs will be trained in the danger signs of asthma: using albuterol inhaler more than every four hours, inability to speak, severe cough, and severe wheeze. If they witness a participant with any of these danger signs, they will call 911 or have the participant's family bring them to seek medical attention immediately. CHWs and RSs will always have

immediate access to a supervisor via cell phone when in the field whom can call if they have concerns or questions.

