Participants that fail the screener or who chose to not provide informed consent will be thanked for their time. Participants that fail the screener but are interested in the study will be offered the option of being put on a re-contact list. If they agree to be put on this list, their contact information will be saved and research staff can call them again in several months to rescreen them. Personal identifying data from the screening (initial and re-contact lists) will be kept in a secure location until recruitment is ended, at which point it will be destroyed. (We will keep their name during the recruitment period only to prevent contacting people who have screened out.) All staff involved in recruitment will receive careful training about the study and the clinic services to ensure that everyone approached understands that participation is voluntary and services at Erie will continue regardless of study participation, and so that Erie staff understands their primary role is patient care. Recruitment will not impinge on clinical responsibilities or clinic operations. Staff involved in recruitment have their time covered by the study. Providers who refer the study to patients do so when they have time and feel comfortable only.

Randomization will be conducted in a 1:1 ratio using randomly mixed permuted blocks of size 4 and 6 to ensure reasonably equal allocation while reducing predictability of the assignment sequence. Upon completion of the randomization assignment, the data management team will generate a letter to the participant informing him/her of their study status and also notify the Erie Intervention Coordinator who will assign the patient to a CHW if randomized to that arm. Although double blinding in a behavioral randomized clinical trial is impossible, blinding will be maximized by: 1) incomplete disclosure of study goals for participants during consent (see Human Subjects for details), 2) blinding outcomes assessors; 3) incomplete disclosure of research hypotheses for non-investigators staff; and 4) training co-investigators and staff in the concept of equipoise. Intervention investigators and staff will be unblinded to treatment arm because they will need to work with the CHWs and monitor intervention fidelity and data accuracy. Study staff and investigators (with the exception of the Safety Officer) will not have access to interim outcomes data.

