8.0 Data Collection and Management Procedures

Data Coordinating Center

Data management for this project will be provided by the Data Coordinating Center (DCC), which is comprised of staff and investigators from the Methodology Research Core in the Institute for Health Research and Policy at UIC. The DCC also serves as the Design and Analysis Core of the University of Illinois at Chicago Center for Clinical and Translational Science (CCTS) which is supposed by NIH funding through a Clinical and Translational Science Award as well as strong institutional commitment. The DCC has extensive experience in the acquisition, maintenance, and analysis of both large and small clinical trial databases. It is directed by [name] who is a co-investigator on this proposal. The DCC faculty and staff are located in same offices as the other UIC investigators. Specific activities of the DCC include: collaborating with the study team to develop a comprehensive, yet efficient, set of case report forms to capture participant data, developing web and direct data capture systems, processing data, implementing and maintaining an effective study database and its associated query system, maintaining a computer environment sophisticated enough to efficiently, effectively, and securely manage the study database, and developing regular reports as to the accuracy and completeness of the study database, participant follow-up, and intervention delivery. The DCC is part of the research team which supports the ready exchange of any needed resources. The DCC will also implement the randomization processes. Access to randomization assignment data will be limited to pertinent DCC staff, intervention staff, and investigators as needed. Outcomes assessors are to remain blind to study arm.

Data acquisition and maintenance

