All interviewer administered questionnaire data will be collected on computers (by outcomes assessors and CHWs) with the possible exception of the mental health instruments. The mental health instruments are to be self-administered for privacy; families will be offered the computer but they will be collected on paper case report forms if caregivers and/or children are uncomfortable answering the questions on the computers. Electronic data collected in the field will be on encrypted computers (see below). Paper forms will be transported to the Institute for Health Research and Policy where outcomes assessors will enter them into the computer data collection program and then store the paper forms in a locked storage cabinet.

All data will be kept confidential, and no subject will be identifiable from research records or published data. We will employ procedures used in other studies to maintain anonymity. All identifying information will be removed from the provider self-report data and all data sheets will be coded with ID numbers only. Tracking information will be stored separately from data files, and access to tracking information will be limited to the PI and research staff. The master list of ID code numbers and corresponding names will be kept in a locked file cabinet or in a password protected file on an internal server, with close scrutiny of access maintained by the PI. The master list is used only to coordinate data collection.

Data will be entered using REDCap (Research Electronic Data Capture). REDCap is a secure, web-based application for building and managing online databases for the collection and entry of research data. It is a valuable resource that allows for the creation of web-based databases quickly and securely, with special features like ad-hoc reporting and scheduling. It is fast and flexible with an easy to use design environment to create data capture forms. The program was developed by staff at Vanderbilt University in 2004 in order to help researchers manage data for small/medium sized projects in a systematic manner (metadata defined, secure, audit trails,

etc). The system is continually updated and enhanced by the Project REDCap team at Vanderbilt. REDCap is maintained by the staff in the DCC.

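### Families are invited to report discomfort with their CHW to the research specialist who must stay blind, which opens a route to unblinding in a subset of CHW-arm families

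*Combined protocol and SAP*

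**What the plan says.** Section 5.0 accepts that double blinding is impossible in this trial and lists four measures to limit the damage. One of them is "2) blinding outcomes assessors". Section 8.0 repeats the rule: "Outcomes assessors are to remain blind to study arm".

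Section 6.8.1 identifies the assessor: "Individual outcomes will be collected in the homes by UIC RS".

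Section 6.8.5, under participant safety, sets the route for complaints: "Participants will be encouraged to notify the RS or project manager if they are uncomfortable with their RS or CHW". If a family does so, "they will be offered the option of changing RSs or CHWs, or withdrawing from the study".

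Section 8.0, under data acquisition, also states: "All interviewer administered questionnaire data will be collected on computers (by outcomes assessors and CHWs", with a possible exception for the mental health instruments. It does not say which questionnaires fall to which group.

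Section 6.7 keeps CHWs out of retention work because "this approach could lead to differential ascertainment of outcomes between the arms and introduce bias into the study".

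**The concern.** The RS has two roles that do not fit together: assessor who must not know the arm, and named recipient of complaints about a worker whom only one arm has. The plan does more than omit a safeguard here. It encourages the disclosure.

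The two primary measures in section 9.0 are days with activity limitation over 14 days and the ACT/cACT. Both depend on reported answers. Families and intervention staff know the arm, so assessor blinding is the main protection left at the point of measurement. The complaint route exists in the CHW arm only, so any bias from it would fall on one side of the comparison. Its direction cannot be predicted.

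Section 6.7 shows that the authors recognise this kind of bias and guard against it elsewhere.

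**Working it through.** No stated sample size, power or alpha bears on this point, so there is no figure to reproduce. The check sets the sections side by side.

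1. **Who must be blind.** Outcome assessors (sections 5.0 and 8.0).
2. **Who the assessor is.** The RS (section 6.8.1).
3. **Who may receive a complaint about a CHW.** The RS or the project manager, as equal alternatives (section 6.8.5).
4. **Who can make such a complaint.** Only families assigned a CHW, which happens only in that arm (section 5.0). From 1 to 4, a CHW complaint made to the RS reveals the allocation to the person who must not know it.
5. **Is there a repair elsewhere?** Limits on access to assignment data (sections 8.0 and 11.3) do not stop a family from speaking at home. The change of RS in section 6.8.5 is an option for the family; a family unhappy with its CHW may change the CHW and keep the same RS. I found no rule that diverts these complaints from the RS, asks families to keep their arm to themselves, or records or handles an unblinded RS.
6. **Is disclosure limited to the CHW arm?** The complaint route is. Disclosure in general is not. Section 5.0 has a letter tell each participant the assignment, and an AE-C family that mentions a clinic session or call (section 6.4.2) reveals its arm just as fully.
7. **Section 8.0 on CHWs as collectors.** Read literally, it conflicts with section 6.8.1. It can also mean the encounter records that CHWs complete under section 6.6, and the instrument table in section 6.8 has an intervention-tracking entry. The text does not settle which is meant.
8. **Order of assessment.** The same table includes an observed home assessment for triggers. It lists asthma control before triggers but does not present this as the order of administration, and no order is stated elsewhere.

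**Size.** For the complaint route, bias in the CHW-arm mean = f × s, where f is the share of that arm whose RS is unblinded by a complaint and s is the average shift in the recorded answer for those children. The arm has 111 to 112 families (section 5.0), and f counts only those who are uncomfortable, report it and choose the RS. The natural yardstick is the planned difference in section 12.0: 2.84 − 2.00 = 0.84 days. The documents give neither f nor s, so I do not express the bias as a share of that difference.

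**The case against.** The strongest reply is that the leak is contingent. A family must be uncomfortable with its CHW, must say so, and must pick the RS although the project manager is equally available. This stands: the risk concerns a subset of the arm.

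Second, the section 8.0 sentence is about medium, computer or paper. It names assessors and CHWs as separate groups and can be reconciled with section 6.8.1 if CHWs enter only their own records. This also stands, so the sentence is an ambiguity to clear up and does not prove a contradiction.

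Third, families know their arm, so respondent bias would survive any change to the RS's role, and a one-item day count leaves limited room for assessor judgement. Both are fair and argue for modest weight. They do not justify a rule that works against a safeguard the plan relies on.

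Fourth, a home with trigger remediation only hints at the arm, since the AE-C also teaches about triggers (section 6.4.2). I agree; asking the primary measures first is a free precaution, not the correction of an error.

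Fifth, the RS may be the easiest contact for a family, and removing one of two contacts from a participant-safety provision has a cost. That is true, and the fix must keep a clear, reachable contact.

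**Conclusion.** The point holds as a conflict between stated rules. Section 6.8.5 invites a disclosure that sections 5.0 and 8.0 require the assessor not to receive, and nothing elsewhere repairs it. The result is a possible route to differential unblinding in a subset of CHW-arm families, of a size the documents do not give. Section 8.0 on CHWs as data collectors needs clarifying, and the lack of any request not to disclose affects both arms.

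Three stronger readings are tempting and are not supported:

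- A reader might infer that the rules as written unblind the primary outcomes across the CHW arm. They do so only where a family complains, and complains to the RS.
- A reader might infer that CHWs collect activity-limitation days or ACT/cACT. No section says so, and section 6.8.1 points the other way.
- A reader might infer that AE-C families cannot be unblinded. They can, in ordinary conversation.

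Nor can the bias be stated as a fraction of the planned effect without inventing both of its terms. The change is worth making because it is cheap and because unblinding that was never recorded cannot be examined later.

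**What to change.** - **Section 6.8.5:** send concerns about a CHW or the AE-C to the project manager or another named person who collects no outcomes, and keep the RS out of that route. The person chosen should not pass the content on to the RS. Concerns about the RS can follow the present route.
- **Sections 5.0 and 6.8.1:** ask families in both arms not to tell the RS which arm they are in or who teaches them about asthma.
- **Section 8.0:** if encounter records were meant, limit CHW data entry to encounter and process records and state that the RS collects all outcome instruments. If something else was meant, reconcile it with section 6.8.1.
- **Section 6.8:** ask activity-limitation days and ACT/cACT before the home observation at each visit.
- **Section 6.8:** have the RS record at each visit whether the arm became known. Where it did, use a different existing RS for later visits if one is available. The documents do not say how many RSs there are, so this should not be an absolute requirement.

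The cost is wording changes, a short request to families, a fixed order for existing instruments and one extra form item, plus some rescheduling where an RS is swapped. The downside is one fewer named contact for concerns about a CHW, so the remaining contact should be easy to reach.
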